The main estimates of effect size from blinded data will be conducted after the outcome measure assessments at the six-month follow-up are complete for all subjects. Data from all doses of MDMA during Stage 1 (n=16), to be compared with all data from placebo sessions (n=8), with each experimental session treated as an independent observation. The MDMA condition will encompass both Group 1 and Group 2 MDMA doses. Estimates of effect size will be obtained from BDI-II, STAI, PSS, IRI, RSES, ERQ, TAS-20, and QoL-Q scores collected pre-treatment, during and after each experimental session, and the follow-up period, with p value set at 0.05. Effect size will be used to determine the appropriate sample size for future studies.

Scores for BDI-II, STAI, PSS, IRI and RSES completed after each of the experimental session will be averaged to produce mean scores for these periods, including a post-experimental session 1 and post-experimental session 2 average score. BDI-II, STAI and PSS scores gathered via postal mail at monthly intervals from two to five months after the second experimental session will be averaged to produce mean scores for the follow-up period. Missing responses will be replaced with the sample average. These averages will be used for estimates of effect size.

TASIT scores will be compared assessing baseline, after experimental session 1, after experimental session 2, at integrative session six and at 6-month follow up. Correlations between TASIT scores and LSAS scores at the time point following each TASIT score will be made to see whether increased awareness of social cues is associated with reduced social anxiety. MDMA dose will be used as a covariate in order to examine the potential relationship between dose and changes in one or more variable, with dose (75, 100 or 125 mg) serving as the covariate.

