2.0 Introduction

This document presents a Statistical Analysis Plan (SAP) for MAPS study protocol MAA-1, a Phase 2 pilot clinical trial designed to evaluate the safety, feasibility, and efficacy of MDMA-assisted psychotherapy in treating social anxiety in adults on the autism spectrum.

The Multidisciplinary Association for Psychedelic Studies (MAPS) is a non-profit research and educational organization working to obtain approval for the prescription use of 3,4-methylenedioxymethamphetamine (MDMA)-assisted psychotherapy in adults on the autism spectrum with social anxiety. This is an initial pilot study to assess the efficacy of MDMA for this indication, following promising results from MAPS-sponsored studies of MDMA-assisted psychotherapy for posttraumatic stress disorder (PTSD).

The Phase 2 pilot study will examine the safety, feasibility, and efficacy of MDMA-assisted psychotherapy for social anxiety in 12 MDMA-naïve adults on the autism spectrum. This study is designed as a dose escalation study to assist with the exploration of safety and finding the most effective dose in this population. Subjects assigned to the MDMA group will receive two of three different doses, either 75 mg, 100 mg, or 125 mg MDMA. Overall, eight subjects (66.7%) will be randomized to the MDMA group and four subjects (33.3%) will be randomized to the placebo group. Subjects who received the placebo during Stage 1 will have the opportunity to cross over and take part in a second study segment, referred to as Stage 2, with two open-label experimental sessions, after completing the six-month follow-up visit at the end of Stage 1.

This study is designed to obtain safety data, and secondarily estimates of effect size for efficacy. The data will be used to determine study design and dosing for future studies for this indication. MAA-1 is also intended to contribute to the development of a manualized psychotherapeutic approach to this potential treatment. This study is exploratory. As a result, the sponsor will perform tests on all statistical comparisons without correcting for multiple comparisons.

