6.0 Sample Size and Power Considerations

This study is a pilot investigation intended to gather preliminary data on the safety and efficacy of MDMA in 12 subjects on the autism spectrum with social anxiety. Because of their exploratory nature, pilot studies are often not powered for detecting the desired effect. Because it is a pilot study in a small sample, results will be used to collect effect size estimates for statistical power calculations for adequately powered subsequent studies.

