8.0 Analyses

In general, nominal variables will be described in terms of frequencies and percentages and analyzed using chi square analysis. Ordinal and non-normal continuous variables will be described using sample median and range, and analyzed by non-parametric statistical tests, and approximately normal variables will be described using sample mean and standard deviations and analyzed by parametric statistical tests. All statistical tests will be two-sided. All p-values will be rounded to and displayed in four decimals. If a p-value less than 0.0001 occurs it will be shown in tables as <0.0001. For any analysis that is called out as parametric, e.g. t-test, the parametric assumptions will be examined. If necessary, nonparametric analyses will be utilized, e.g. Wilcoxon rank-sum test.

Clinical data will be presented in tabular format. Data not subject to analysis according to this plan will not appear in any tables or graphs, but will be included in the data listings. Analyses will be carried out with SAS Version 9.3 or higher. Selected results may be presented graphically using standard graphical software.

Post-hoc exploratory analyses not identified in this SAP may be performed to further examine the study data. These analyses will be clearly identified as such in the final clinical study report.

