8.10.1 Primary Efficacy Analyses

Liebowitz Social Anxiety Scale (LSAS)

The primary efficacy evaluation is the change from baseline to the primary outcome timepoint (visit 13, one month post experimental session 2) in the LSAS score of Social Anxiety (difference score). The primary efficacy comparison on difference scores will be made with independent sample t-tests at an alpha level of 0.05. If the primary hypothesis rejects, pairwise comparisons among the treatment groups will be made with t-tests. If the parametric assumptions for the t-test analyses are not met, the analogous nonparametric methods will be used (Wilcoxon Rank Sum Test). If data has normal distribution, Cohen's d placebo-subtracted effect size will be estimated on mean difference scores from baseline to Visit 13 with confidence intervals.

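### The LSAS effect size and its confidence interval depend on a normality judgement that 8 vs 4 subjects cannot support, no effect measure is named otherwise, and no small-sample correction is stated

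*SAP*

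**What the plan says.** SAP 8.10.1 compares the change in LSAS from baseline to Visit 13 by "independent sample t-tests at an alpha level of 0.05", with a Wilcoxon rank sum test if the parametric assumptions fail. The effect size comes last and is conditional: "If data has normal distribution", a Cohen's d "placebo-subtracted effect size will be estimated on mean difference scores from baseline to Visit 13 with confidence intervals". No effect measure is named for the Wilcoxon branch. Neither document says which standard deviation standardises d or mentions a small-sample correction.

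Two other places carry no condition. SAP 8.10.2 says the LSAS total score will also have a Cohen's d. Protocol 12.0 says effect sizes for all outcome measures will be estimated by Cohen's methods.

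Both documents say what the estimate is for. Protocol 12.0: "Effect size will be used to determine the appropriate sample size for future studies". SAP 6.0: "results will be used to collect effect size estimates for statistical power calculations for adequately powered subsequent studies". Protocol 3.1 makes estimating the LSAS effect size the primary objective.

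**The concern.** There are two linked problems.

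- **The condition.** The placebo-subtracted estimate and its interval are what a later power calculation needs, yet 8.10.1 lets them depend on how 12 observations look. No normality test or threshold is named. The instruction also conflicts with SAP 8.10.2 and Protocol 12.0, so two analysts could follow the plan and deliver different outputs.
- **The estimator.** Cohen's d as usually computed overstates the true standardised difference on average in small samples. A value that is too high on average, put into a sample size formula, gives a trial that is on average too small.

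**Working it through.** The documents give no assumed effect, SD, power or sample size derivation (Protocol 12.1 says power estimates were not available), so there is no planned figure to reproduce.

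**Inputs**

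- Allocation, SAP 2.0: "Overall, eight subjects (66.7%) will be randomized to the MDMA group and four subjects (33.3%) will be randomized to the placebo group". 8/12 = 66.7% and 4/12 = 33.3%, as stated. Degrees of freedom: 8 + 4 − 2 = 10.
- Alpha 0.05 (SAP 8.10.1) and, from SAP 8.0, "All statistical tests will be two-sided".
- Protocol 5.4: subjects lost after the first experimental session are not replaced, so the degrees of freedom can fall below 10. No dropout rate is given.
- My assumptions: true d of 0.5 to 1.5, a 1:1 next trial, 80% power.

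**Mean bias of d**

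With m degrees of freedom, E[d] = δ / J(m), where J(m) = Γ(m/2) / [√(m/2) · Γ((m−1)/2)].

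J(10) = Γ(5) / [√5 · Γ(4.5)] = 24 / (2.2361 × 11.6317) = 0.923.

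| Setting | df | J | Mean inflation of d (1/J − 1) | Factor on n (J²) |
|---|---|---|---|---|
| 8 vs 4 subjects | 10 | 0.923 | 8.4% | 0.851 |
| Two subjects lost | 8 | 0.903 | 10.8% | 0.815 |
| 16 vs 8 sessions (Protocol 12.0, sessions treated as independent) | 22 | 0.965 | 3.6% | 0.932 |

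**Effect on the next trial**

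Required n varies as 1/d², so using δ/J in place of δ multiplies n by J² = 0.851, a cut of about 15%. For true d = 0.8, the two-sided t-test at 80% power needs 25.5, so 26 per arm. At 0.8/0.923 = 0.867 it gives 21.9, so 22 per arm. True power with 22 per arm is 73.6%.

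**Bias against sampling error**

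At 8 vs 4, d·√(8·4/12) follows a noncentral t with 10 df. At true d = 0.8:

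- mean of d 0.867, so bias 0.067;
- SD of d 0.72, about 11 times the bias;
- median of d 0.821, or 2.6% high;
- central 95% of estimates −0.42 to 2.43;
- d exceeds the truth in 51% of trials, Hedges' g in 47%;
- root mean squared error 0.72 for d and 0.66 for g.

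Over true d of 0.5 to 1.5 the bias is 0.04 to 0.13 and the SD of d is 0.70 to 0.80.

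An observed d of 0.8 corresponds to t = 0.8 × 1.633 = 1.31 and a noncentral-t 95% interval of −0.47 to 2.03.

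**How well normality can be judged**

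The plan names no test, so I assumed Shapiro-Wilk at 0.05 in each arm (3,000 simulated data sets of 8 and 4). Truly normal data failed in at least one arm 9.7% of the time. Exponential data, which are strongly skewed, failed in at least one arm 42.4% of the time and so passed in both 57.6% of the time. In the placebo arm alone, exponential data were rejected 13.1% of the time.

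**The case against.** A reader might infer that the effect size will be missing altogether if the data look non-normal. The documents do not support that. SAP 8.10.2 and Protocol 12.0 ask for Cohen's effect size unconditionally, and SAP 8.10 lists mean and SD by group, from which d or g can be computed. That rescue is partial. SAP 8.0 describes non-normal continuous variables by median and range, so it is unclear whether means and SDs would be shown in that case. The LSAS sentence in 8.10.2 does not mention an interval. If the interval is carried over because secondary analyses follow the primary methodology, the condition arguably comes with it.

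A weak normality check also rarely rejects, so withholding is the less likely error and a d reported on skewed data the likelier one. That is correct. It shows that the condition protects little; it does not justify keeping it.

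The strongest objection is that the bias is trivial beside the imprecision, that g barely changes the chance of overestimation (47% against 51%), and that the real danger is planning on any point estimate from 12 subjects. This stands, and it rules out saying that the next trial would be undersized. It also argues for giving the interval always, which 8.10.1 does not do.

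Two smaller points also stand. That d is uncorrected is inferred from the name, since no formula is given. And the effect size is not simply the trial's main output: Protocol 3.1 makes it the primary objective, but Protocol 12.0 calls the trial primarily a safety study and SAP 2.0 puts effect size second.

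**Conclusion.** The point holds as an inconsistency, a missing fallback measure and an unstated correction. SAP 8.10.1 conditions the estimate and interval on something 8 vs 4 subjects cannot show, and disagrees with SAP 8.10.2 and Protocol 12.0.

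If d is computed without correction, its mean bias is 8.4% at 10 df and 10.8% at 8 df. Planning on its expected value would cut n by about 15% at 10 df. The 26-to-22 example, with true power about 74%, rests on an assumed true d of 0.8 and 80% power. The 10 df figure assumes one value per subject; the protocol's session-level count would give 3.6%. Because sampling error at true d = 0.8 is about 11 times the bias, this is a tendency in the mean, and the correction is a modest improvement. The simulated pass rates rest on an assumed test.

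**What to change.** 1. In SAP 8.10.1, delete the normality condition on the effect size, and bring 8.10.1, 8.10.2 and Protocol 12.0 into line.
2. Always report the raw MDMA-minus-placebo difference in mean LSAS change with a 95% interval, and Hedges' g with a noncentral-t 95% interval. State that the standardiser is the pooled SD of change. Apply the same rule to the secondary scales.
3. When the Wilcoxon test is used, add a rank-based effect measure with an interval, for example the Hodges-Lehmann shift.
4. State that later trials will be sized from the corrected estimate together with its interval, not from the point estimate alone.

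No new data or procedures are needed; the change is to the plan's wording. The reported standardised effect becomes about 8% smaller (an observed d of 0.8 becomes g = 0.923 × 0.8 = 0.74).

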8.10.2 Secondary Efficacy Analyses

The secondary efficacy analyses will be made with independent sample t-test comparing change from baseline (Baseline) to the primary outcome timepoint (visit 13, one month post experimental session 2) of all the secondary measures, following the same methodology used for the primary endpoint. If the parametric assumptions for the t-test analyses are not met, the analogous nonparametric methods will be used (Wilcoxon Rank Sum Test).

Liebowitz Social Anxiety Scale (LSAS) composite scores will be analyzed in the same manner as the LSAS total score primary analysis, and LSAS total score will also be analyzed for effect size with Cohen's *d* analysis.

Perceived Stress Scale (PSS) total score will be analyzed in the same manner as the LSAS total score primary analysis.

Beck Depression Inventory-II (BDI-II) total score will be analyzed in the same manner as the LSAS total score primary analysis.

Interpersonal Reactivity Index (IRI) composite scores will be analyzed in the same manner as the LSAS total score primary analysis.

Rosenberg Self Esteem Scale (RSES) total score will be analyzed in the same manner as the LSAS total score primary analysis.

State Trait Anxiety Index (STAI) subscale scores will be analyzed in the same manner as the LSAS total score primary analysis.

The Awareness of Social Inference Test (TASIT) composite and total scores will be analyzed in the same manner as the LSAS total score primary analysis.

Toronto Alexithymia Scale 20 (TAS-20) total score will be analyzed in the same manner as the LSAS total score primary analysis.

Emotional Regulation Questionnaire (ERQ) composite scores will be analyzed in the same manner as the LSAS total score primary analysis.

Quality of Life Questionnaire (QoL-Q) composite and total scores will be analyzed in the same manner as the LSAS total score primary analysis.

Biomarker (oxytocin, vasopressin, and cortisol) levels will be analyzed in the same manner as the LSAS total score primary analysis.

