4.1 Planned Duration of Study

- Subjects in Stage 1 and follow-up: 8 months
- Subjects in Stage 1, follow-up, and Stage 2: 10 months

These lengths of time do not include screening, which may take up to two months. The total duration of the study will depend on enrollment rates, but is expected to last at least 22 months. Any delay between visits would result in a corresponding extension of study duration.

Table 2. Time & Events Stage 1

Study Phase	Baseline		Preparatory Sessions			Experimental Session	Integrative Sessions			Experimental Session	Integrative Sessions			Follow-up	6-Month Follow-up
	V1	V2	V3	V4	V5	V6	V7	V8	V9	V10	V11	V12	V13	(remote)	V14
Visit Timing			Week 1	Week 2	Week 3		1 day later	2 Wks later	2 Wks later	Apr. 1 Month after V6	1 day later	2 Wks later	2 Wks later	Monthly By Mail	6 Months after V10
Informed Consent	✓														
Medical/Psychiatric History & Evaluation	✓														
SCID	✓														
General Physical Exam (includes neurological)		✓													
Screening Clinical Lab Tests, EKG		✓													
ADOS-2		✓ ^H													
LSAS		✓ ^{G,H}					✓ ^G	✓ ^G	✓ ^G		✓ ^G	✓ ^G	✓ ^G		✓ ^G
C-SSRS		✓			✓	✓ ^{A,C,D}	✓ ^E	✓	✓	✓ ^{A,C,D}	✓ ^E	✓	✓		✓
Feedback Questionnaire, Qualitative Interview		✓													✓
Study Enrollment if Eligible			✓												
Collect Concomitant Medication	✓		✓	✓	✓	✓	✓	✓	✓	✓	✓	✓	✓		✓
Start Medication Taper (if applicable)			✓												✓ ^I
Collect Serology Samples (OT, AVP, CORT)		✓								✓			✓		✓
Record to Video			✓	✓	✓	✓	✓	✓	✓	✓	✓	✓	✓		✓
General Wellbeing			✓	✓	✓	✓	✓	✓	✓	✓	✓	✓	✓		✓
Pregnancy Screen (if applicable), Drug Screen		✓				✓				✓					
BDI-II, STAI			✓				✓	✓	✓		✓	✓	✓	✓	✓
PSS			✓				✓				✓		✓	✓	✓
IRI, RSES			✓				✓				✓		✓		✓
TASIT				✓		✓				✓			✓		✓
ERQ, TAS-20					✓								✓		✓
QoL-Q					✓										✓
Administer Drug + Therapy						✓				✓					
Monitoring of BP, Pulse, and Temperature, SUD						✓ ^{A,B,C}				✓ ^{A,B,C}					
Belief of Condition Assignment							✓				✓				
Integrative Therapy Session							✓	✓	✓		✓	✓	✓		
Start 7 Days Phone Contact							✓				✓				
Spont. Reported Reactions & All Adverse Events						✓	✓ ^F	✓		✓	✓ ^F	✓			
Symptoms at Baseline	✓		✓	✓	✓	✓	✓	✓	✓	✓	✓	✓	✓		✓
Adverse Events Requiring Doctor's Visit			✓	✓	✓	✓	✓	✓	✓	✓	✓	✓	✓		✓
Adverse Events Causing Withdrawal, SAEs			✓	✓	✓	✓	✓	✓	✓	✓	✓	✓	✓	✓	✓
Unblinding & Termination															✓ ^J
Approximate Hours for Study Visit	3	1.8	1.5	1.5	1.8	8.0	1.9	1.7	2.1	8.0	1.9	1.7	2.6	0	2.2

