A = At the beginning of the session; B = Approximately every sixty minutes; C = As needed; D = Approximately six hours post drug; E = Day 2 and Day 7 phone calls only; F = Reactions collected for seven days post experimental session; G = Independent Rater administered; H = May be recorded to video; I = Stage 2 subjects only; J = Only MDMA subjects will terminate.

Table 3. Time & Events Stage 2

Study Phase	Experimental Session	Integrative Sessions			Experimental Session	Integrative Sessions		
	V15	V16	V17	V18	V19	V20	V21	V22
Visit #	V15	V16	V17	V18	V19	V20	V21	V22
Visit Timing		1 day later	2 Wks later	2 Wks later	Appr. 1 Month after V15	1 day later	2 Wks later	2 Wks later
LSAS		✓ ^G	✓ ^G	✓ ^G		✓ ^G	✓ ^G	✓ ^G
C-SSRS	✓ ^{A, C, D}	✓ ^E	✓	✓	✓ ^{A, C, D}	✓ ^E	✓	✓
Feedback Questionnaire, Qualitative Interview								✓
Collect Concomitant Medication	✓	✓	✓	✓	✓	✓	✓	✓
End Medication Taper (if applicable)	✓ ^I							
Collect Serology Samples (OT, AVP, CORT)	✓			✓	✓			✓
Record to Video	✓	✓	✓	✓	✓	✓	✓	✓
General Wellbeing	✓	✓	✓	✓	✓	✓	✓	✓
Drug Screen	✓				✓			
Pregnancy Screen (if applicable)	✓				✓			
BDI-II, STAI		✓	✓	✓		✓	✓	✓
PSS		✓				✓		✓
IRI, RSES		✓				✓		✓
TASIT	✓				✓			✓
ERQ, TAS-20								✓
Administer Drug + Therapy	✓				✓			
Monitoring of BP, Pulse, and Temperature, SUD	✓ ^{A, B, C}				✓ ^{A, B, C}			
Integrative Therapy Session		✓	✓	✓		✓	✓	✓
Start 7 Days Integrative Phone Contact		✓				✓		
Spont. Reported Reactions & All Adverse Events	✓	✓ ^F	✓		✓	✓ ^F	✓	
Symptoms at Baseline	✓	✓	✓	✓	✓	✓	✓	✓
Adverse Events Requiring Doctor's Visit	✓	✓	✓	✓	✓	✓	✓	✓
Adverse Events Causing Withdrawal	✓	✓	✓	✓	✓	✓	✓	✓
SAEs	✓	✓	✓	✓	✓	✓	✓	✓
Termination								✓
Approximate Hours for Study Visit	8.0	1.9	1.7	2.1	8.0	1.9	1.7	2.7

A = At the beginning of the session; B = Approximately every sixty minutes; C = As needed; D = Approximately six hours post MDMA; E = Day 2 and Day 7 phone calls only; F = Reactions collected for seven days post experimental session; G = Independent Rater administered; H = May be recorded to video; I = At least 5 half-lives and 1 week before the experimental session.

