The QoL-Q is a 40-item measure of quality of life. It is administered as an interview and assesses eight domains [151]. The QoL-Q assesses the following domains; self-determination, (autonomy and decision-making), social inclusion (acceptance by others within the community, supports), material well-being (financial security and socioeconomic status), personal development (education, skills and competence), emotional well-being (spirituality, happiness, sense of safety) interpersonal relations (intimacy, affection, friendship), rights (voting, privacy, legal rights and protections) and physical well-being (health, nutrition, mobility). It is estimated to take between a half hour to an hour to complete the QoL-Q. It can be used in diverse populations, including autistics and other developmentally disabled people [152, 153]. The measure has excellent internal reliability ($\alpha = 0.90$) and strong test-retest reliability ($\alpha = 0.87$). The QoL-Q will be completed according to the Time and Events table.

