5.2.2 Preparatory Sessions and Baseline Measures

Subjects who do not complete all screening activities will not be enrolled. Eligibility may be discussed by phone after screening is complete and at the time Visit 3 is scheduled but the final confirmation will occur at Visit 3. If all inclusion criteria and no exclusion criteria are met, eligibility will be confirmed with the subject.

- Complete a final review of inclusion/exclusion criteria.
- Assess general wellbeing.
- Confirm eligibility and willingness to participate in study.
- Enroll subject and issue subject number.
- Ensure medical history and medication history is complete. After enrollment new events will be collected as AEs and new medications, as described in Section 8.5 and Section 9.0.
- Assess status of symptoms at baseline specific to the study population.
- Discuss medication tapering, if applicable. Upon confirmation of eligibility, the PI will consult the prescribing physician to initiate medication tapering for

subjects who must refrain from taking a psychiatric medication for the study. Tapering will follow a time course appropriate for the medication given its half-life, with the first experimental session scheduled to occur after complete washout.

The subjects will undergo three preparatory sessions lasting approximately sixty minutes each with their therapist team, prior to their first experimental session. The first preparatory session will take place at Visit 1 after enrollment confirmation. Baseline measures will be spread out among preparatory sessions in order to reduce participant fatigue from completion of measures.

The therapists will work with the subject to prepare for MDMA-assisted therapy. The therapists and subject will seek to form a strong working relationship with each other as the therapists help the subject prepare for upcoming experimental sessions. Preparatory sessions will promote a safe set and setting for confronting emotions and are intended to develop therapeutic alliance.

During preparatory sessions:

- a. Therapists may record all sessions to audio and video. Subjects may access video recordings from these sessions upon request via a secure and password protected website.
- b. Collect AEs and medications, as described in Section 8.5 and Section 9.0.
- c. Assess status of symptoms at baseline specific to the study population.

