- d. The therapists will inquire about any possible changes in the subject's health to ensure that subject continues to meet eligibility criteria and, if applicable, will confirm that the subject has appropriately tapered off of medications.
- e. The subject and therapists will discuss goals for the experimental session and will review what will happen during the experimental session.
- f. During one of the preparatory sessions, the therapists will introduce the subject to the staff at the outpatient research center who they will be most likely to encounter before, during, or after treatment sessions.
- g. The Support Partner will meet with the therapists prior to the first experimental session to review and confirm their role and responsibilities and sign an ICF addendum. There must be mutual agreement between the subject and therapists concerning the presence of the Support Partner.
- h. The therapists will administer the C-SSRS just prior to beginning the second preparatory session, unless a subject is still undergoing medication washout. Subjects still undergoing medication washout will complete the C-SSRS during the second preparatory session or at a point after washout is complete prior to the first experimental session.
- i. Assess general wellbeing at each preparatory session.
- j. At the end of the first preparatory session, subjects will complete:
 - a. BDI-II
 - b. STAI
 - c. PSS
 - d. IRI

- e. RSES
- k. At the end of the second preparatory session, subjects will complete the TASIT.
- l. The second preparatory session will include a comprehensive tour of the treatment location and introductions to all available research and support personnel who subjects are likely to see during experimental sessions.
- m. At the end of the third preparatory session, subjects will complete:
 - a. ERQ
 - b. TAS-20
 - c. QoL-Q
- n. During the third and last preparatory session, give the Reminder of Study Rules to the subject, which includes instructions and restrictions for conduct prior to receiving the drug. Subjects must agree to:
 - Refrain from eating after 24:00 (midnight) the evening before the experimental session.
 - Ingest only alcohol-free liquids after 24:00 (midnight) the evening before the experimental session.
 - Refrain from the use of any psychoactive drug, with the exception of caffeine or nicotine, within 24 hours of each experimental session.

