- l. Assess status of symptoms at baseline specific to the study population.
- m. Remind the subject that the last integrative session in Stage 1 that this will be the last in-person visit prior to the 6-month Follow-up visit, and that some measures will be collected monthly by mail.
- n. Review how to use the Memory Aid Card with the subject. Subjects will use this card to record AEs, medications, and changes in psychiatric status that they will be asked about at the 6-month follow-up visit. Memory Aids will not be collected.

5.2.7 6-Month Follow-up

Subjects who have withdrawn from treatment but have continued for follow-up will also complete these assessments whenever possible. During the follow-up period:

- a. Subjects may return to taking psychiatric medications or change frequency or method of psychotherapy received from outside therapists if necessary.
- b. The following self-report measures will be completed by subjects and collected monthly at two, three, four, and five months after the second experimental session by mail:
 - a. BDI-II
 - b. STAI
 - c. PSS
- c. At the 6-month follow-up, an in-person visit will be conducted.
- d. The IR will administer the LSAS.
- e. Collect information on phase of menstrual cycle for female subjects.
- f. Blood will be drawn for biomarker analysis.
- g. Subjects will complete self-report outcome assessments, including:
 - a. ERQ
 - b. TAS-20
 - c. TASIT
 - d. QoL-Q
 - e. RSES
 - f. IRI
 - g. BDI-II
 - h. STAI
 - i. PSS
 - j. Feedback Questionnaire
- h. Review specified AEs and medications as described in Section 8.5 and Section 9.0. Subjects should bring the Memory Aid Cards to this visit, to be used as aids in recollection. These cards will not be collected.
- i. Assess status of symptoms at baseline specific to the study population.
- j. One of the therapists will assess suicidality with the C-SSRS.
- k. General wellbeing will be assessed.
- l. The therapists will review the responses to the Feedback Questionnaire assessing effects of the study with the subject. During the qualitative interview, additional follow-on questions may be asked to elucidate self-reported responses on the questionnaire.
- m. After all assessments are complete, the therapists will break the blind for the individual subject.
- n. Subjects who were randomized to the MDMA group will complete the termination visit at this time.

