8.10.2.1 Secondary Efficacy Analyses at Secondary Endpoints

Crossover Subject Analyses

LSAS data from subjects assigned to the placebo group, i.e. ‘crossover population,’ will be analyzed by t-tests on difference scores from Stage 1 endpoint (Visit 13) to Stage 2 endpoint (Visit 22) only if there is sufficient data to examine.

6-month Follow-up Analyses

To determine durability of effects, LSAS data will be analyzed by t-tests on difference scores from Stage 1 endpoint (Visit 13) to 6-month follow-up. Additionally, the following measures’ scores will be analyzed in this same fashion: PSS, BDI-II, IRI, RSES, STAI, TASIT, TAS-20, ERQ, QoL-Q

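### Both QoL-Q analyses in the SAP need a Visit 13 score that the Protocol's schedule does not collect

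*SAP*

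**What the plan says.** SAP 8.10.2 sets one contrast for every secondary measure: change from baseline to Visit 13, compared between groups by t-test or its rank-based substitute. It then goes through the measures one by one, and for this one says "Quality of Life Questionnaire (QoL-Q) composite and total scores will be analyzed in the same manner as the LSAS total score primary analysis". SAP 8.10.1 confirms that the LSAS method is a baseline to Visit 13 difference score.

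SAP 8.10.2.1 adds a durability analysis of change from Visit 13 to the 6-month follow-up. It first describes this for LSAS, then says that further "scores will be analyzed in this same fashion: PSS, BDI-II, IRI, RSES, STAI, TASIT, TAS-20, ERQ, QoL-Q".

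For timing, Protocol 5.1.2 defers to the schedule: "The QoL-Q will be completed according to the Time and Events table". The relevant schedule is "Table 2. Time & Events Stage 1", in Protocol 4.1. Protocol 5.2.2 explains why first assessments fall at different visits: "Baseline measures will be spread out among preparatory sessions in order to reduce participant fatigue from completion of measures". QoL-Q is placed last, in the list that opens "At the end of the third preparatory session, subjects will complete", together with ERQ and TAS-20. Protocol 5.2.7 lists it again at the 6-month visit.

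**The concern.** Each QoL-Q analysis in the SAP subtracts a Visit 13 score from something, or something from a Visit 13 score. If no QoL-Q is taken at Visit 13, both difference scores are undefined for every subject who follows the schedule. The blanket wording that gives all secondary measures the LSAS method seems to have been applied without checking each measure against the visit table.

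What is at stake is limited. QoL-Q would be collected from all subjects, at half an hour to an hour per interview by the Protocol's own estimate, and then have no usable prespecified comparison. The analyst would fall back on a contrast that the SAP does not name, and SAP 8.0 and 8.10.3 require such analyses to be labelled post hoc. Yet the Protocol's introduction makes quality of life one of the study's focuses, and Protocol 12.0 foresees QoL-Q effect sizes from pre-treatment and follow-up scores.

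**Working it through.** No power or sample-size figure is involved. The check is whether both ends of each planned contrast are collected.

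**Inputs.** Protocol Table 2 has 15 visit columns: V1 to V13, the remote monthly contact, and V14. For each measure I took the first pre-treatment visit and whether V13 and V14 are ticked.

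| Measure | First pre-treatment visit | V13 | V14 | Baseline to V13 | V13 to V14 |
|---|---|---|---|---|---|
| LSAS | V2 | yes | yes | computable | computable |
| BDI-II, STAI, PSS, IRI, RSES | V3 | yes | yes | computable | computable |
| TASIT | V4 | yes | yes | computable | computable |
| ERQ, TAS-20 | V5 | yes | yes | computable | computable |
| **QoL-Q** | **V5** | **no** | **yes** | **not computable** | **not computable** |

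The rows cover 1 + 5 + 1 + 3 = 10 measures, all of those in SAP 7.1. The biomarkers (V2, V10, V13, V14) also have a V13 sample. QoL-Q is the only measure without a V13 value.

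**Is the table misread?** The QoL-Q ticks are in columns 5 and 15. The adjacent ERQ/TAS-20 row has ticks in columns 5, 13 and 15, so the V13 column survived extraction and the QoL-Q cell in it is empty. The visit text agrees with the ticks: QoL-Q is listed at the third preparatory session (5.2.2) and at the 6-month visit (5.2.7). It is absent from the integrative-session list in 5.2.6, but that is weak evidence, because the same list omits PSS, IRI and RSES, which Table 2 does tick at V13.

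**Counts.** Scheduled QoL-Q assessments: 2 per subject × 12 subjects = 24, of which 0 are at V13. The Stage 2 schedules (Table 3 in the Protocol and in the SAP) have 25 procedure rows each, and none names QoL-Q.

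**Do the missing-data rules help?** SAP 8.2 only moves early-termination data to a nearby visit. At most it could place an occasional withdrawn subject's score at V13, and it creates nothing for completers. Protocol 12.0 replaces missing responses with the sample average, but there is no V13 sample to average.

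**What remains.** V5 to V14 gives up to 12 change scores, 8 MDMA and 4 placebo. V13 falls 1 + 14 + 14 = 29 days after V10, or about 1 month, and V14 falls 6 months after V10. The contrast therefore ends about 6 − 1 = 5 months after the primary timepoint.

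**The case against.** The strongest reply is that the SAP may follow a different schedule. Its Stage 1 Time and Events table is missing from the supplied text, and that gap is not an error in the plan. The SAP departs from this Protocol elsewhere: it adds BDNF, tabulates condition guesses by the independent raters, and mentions a 6-month follow-up after Stage 2. A V13 QoL-Q in the missing table cannot be ruled out. Against this, the surviving end of the SAP's table footnote is word for word that of Protocol Table 2 ("H = May be recorded to video; I = Stage 2 subjects only; J = Only MDMA subjects will terminate"), which suggests the same schedule without proving it. This part of the objection stands as a limit: the finding is about the Protocol's schedule.

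Second, Table 2 is not a perfect record of intent. The objectives call for ERQ and TAS-20 a month after both sessions and for biomarkers at both sessions, but Table 2 has no V9 tick for the former and no V6 tick for the latter. Protocol 12.0 also speaks of QoL-Q scores from during and after the sessions. That sentence covers eight instruments at once, however, and schedules nothing. For QoL-Q, the table and the visit text agree with each other and differ from that sentence.

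Third, Protocol 5.2.8 promises Stage 2 subjects the same evaluations as Stage 1, so the count of 24 reflects the tables only. Any extra Stage 2 assessment would still not be a V13 score.

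Fourth, SAP 8.10 already provides descriptive statistics by group, so the QoL-Q data would not go unreported. That is true, but descriptive statistics are not the between-group change analysis that the SAP promises. It is also true that QoL-Q is in no listed objective.

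**Conclusion.** The concern holds. Under the only Stage 1 schedule in the documents, 2 of the 2 QoL-Q analyses named in the SAP cannot be computed, because 0 of 24 scheduled assessments fall at Visit 13. This affects 1 of the 10 outcome measures in SAP 7.1. The conclusion assumes that the SAP's missing Stage 1 table matches Protocol Table 2.

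The severity is minor. The study is an exploratory pilot, and the LSAS primary analysis and the other secondary measures have the visits they need. Only one QoL-Q time contrast is available, so there is little room for choosing a contrast after seeing the data. The loss is that this contrast is not prespecified.

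**What to change.** Four wording changes are enough:

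- **SAP 8.10.2:** take QoL-Q out of the blanket Visit 13 rule and define its analysis as the between-group difference in change from V5 to V14, reported as an estimate with its confidence interval. V14 is still blinded, since Protocol 5.2.7 says "After all assessments are complete, the therapists will break the blind for the individual subject". Note beside the result that medication and outside therapy are allowed to change during follow-up.
- **SAP 8.10.2.1:** remove QoL-Q from the list for change from Visit 13 to 6 months.
- **SAP 8.6:** define baseline as each measure's pre-treatment visit in the schedule (V2 to V5 depending on the measure, V5 for QoL-Q). The present text points to the screening/baseline visit, and Table 2 uses the baseline label only for V1 and V2.
- **Protocol 12.0:** bring the sentence on QoL-Q timing into line with Table 2.

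This needs no new visits or data. The cost is that the QoL-Q comparison falls about 5 months after the primary timepoint, when other treatment may have changed. If a result at the primary timepoint is wanted, the alternative is to add QoL-Q at V13. That would need a Protocol amendment and a further interview of half an hour to an hour per subject, and it would only help for subjects who have not yet passed that visit.
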